8.3 Demographics, Baseline Characteristics and Concomitant Medications

Demographic data and patient characteristics at baseline will be summarized descriptively.

Frequency and percentage of prior and concomitant medication use will be summarized by World Health Organization (WHO) Drug dictionary coded terms - Anatomic Therapeutic Chemical (ATC) classification and preferred term.

8.4 Treatment Compliance

Summary statistics for the number of N-Acetyl-L-Leucine doses taken, based on bottles of Study Drug dispensed and return bottle counts, will be calculated for each visit. Overall compliance in terms of the percentage of drug taken based on these data will be summarized descriptively together with the proportion of patients who take at least 80% of the prescribed medication.

8.5 Efficacy Analyses

The primary analyses of efficacy will be based on the mITT. Analyses of efficacy based on the PPS will also be undertaken to provide supplementary information.

For each of the primary and secondary endpoints there will be separate analyses within key subgroups. The subgroups to be considered will be defined by:

- Naïve versus non-naïve as determined at screening
- Age (pediatric versus adult)
- Age/weight/dosing group
- Age of diagnosis (Infantile, Juvenile, Adult)
- Disease severity based on SARA below/ above the median SARA score at Visit 1
- Gender (male versus female)
- Region (US versus Europe)
- Primary Anchor Test (9HPT-D or 8MWT)
- Tay-Sachs versus Sandhoff patients
- Individual components of SARA scale: Gait Subtest
- Composite of SARA Subtests 1-4 (Gait, Stance, Sitting, Speech)
- Intra-patient variability between SARA score at Visit 1 (Baseline 1) versus Visit 2 (Baseline 2) (below/above median).
- Intra-patient variability between CI-S score Visit 1 (Baseline 1) versus Visit 2 (Baseline 2) (below/above median).

Additional subgroups can be added at the time of analysis on an exploratory basis.

Separate trials are planned to be conducted with N-Acetyl-L-Leucine for NPC, GM2gangliosidosis, and ataxia-telangiectasia. There will however be a planned series of metaanalyses that will bring together the data from the studies for the primary and selected secondary endpoints. Further details will be provided in an MASAP.

8.5.1 Primary Efficacy Endpoint

The primary endpoint for the study is based on blinded raters' Clinical Impression of Change in Severity (CI-CS) comparing videos showing the patient's change in performance over 42 days (+7 days) on a pre-defined anchor clinical symptom scale: either the 9 Hole Peg Test of the Dominant Hand (9HPT-D) or the 8 Meter Walk Test (8MWT). A manual will be provided to each clinical site, which provides instructions for the administration of the CI-CS [Fields, 2020]. Similarly, a video-acquisition manual will be provided, which provides instructions for making standardized videos of the 8MWT and 9HPT-D primary anchor tests The comparison of the Visit 4 video with the Visit 2 video and the comparison of the Visit 6 video with the Visit 4 video will provide the scores that contribute to the primary endpoint. Each of these comparisons will score change on a 7-point Likert scale (+3=significantly improved to -3= significantly worse).

During the pre-treatment period, the treating physician will evaluate each patient's clinical symptoms and select, at **Visit 1**, either the 9HPT-D or 8MWT as the primary anchor around which the CI-CS assessment will be scored. A cognitive assessment should be performed at **Visit 1** according to standard procedures of the clinical site to assist with the selection of the anchoring functional test appropriate for each patient from both a cognitive and a motor perspective.

The primary evaluation of the CI-CS will be performed by two independent raters whose assessments will be based on videos of the anchor test taken at each visit. These raters will be blinded to the treatment periods (baseline, treatment, or washout) to reduce detection and performance bias.

The primary endpoint is defined as the CI-CS comparing end of treatment with N-Acetyl-L-Leucine (Visit 4) with baseline (Visit 2) minus the CI-CS comparing the end of washout (Visit 6) with the end of treatment with N-Acetyl-L-Leucine (Visit 4) based on the primary anchor test.

The CI-CS assessment will instruct the blinded rater to consider: 'compared to the first video, how has the severity of their performance on the 9HPT-D or 8MWT changed (improved or worsened) in 6-weeks as observed in the second video?'

Each video pairing (CI-CS) will be read by the two independent raters, and the appropriate Likert scale score will be entered onto the eCRF. If there is a difference of one (1) point in the two primary blinded reviewers' CI-CS scores for a specific video pairing, the two scores will be averaged. If there is difference greater than one (1) point between the two primary blinded reviewers' CI-CS scores for a specific video pairing, an adjudication read will be triggered. In such cases, a third blinded reviewer will review the scores given from each of the two primary independent reviewers and determine which score is more accurate, that of reviewer A or reviewer B (adjudication by consensus). The adjudicator's decision will be the final score for that video assessment.

The statistical analysis of this endpoint will utilize a single sample t-test comparing the mean value of the primary endpoint with zero. This endpoint allows the effect N-Acetyl-L-Leucine to be measured both in terms of improvement during treatment followed by any deterioration once treatment is removed.

Summary statistics will in addition be calculated separately according to subgroups defined by the primary anchor test

8.5.2 Secondary Efficacy Endpoints

A key Secondary Endpoint that will be evaluated to directly supplement the analysis of the primary endpoint is based on the independent raters' Clinical Impression of Severity (CI-S) of each video.

The independent raters will be given 6 videos of the patient's performance of the primary anchor test taken at Visit 1 to Visit 6. The videos will be labeled as Video A, B, C, D, E, F. The videos will be presented in a random order, and the independent raters will be blinded to the timepoint corresponding to each video.

For each video, the independent raters will make their evaluation of the CI-S, which asks: "Considering your total clinical experience with this particular population, how ill is the patient at this time?"

The CI-S is rated on a 7-point Likert scale ranging from + 3 (normal, not at all ill) to -3 (among the most extremely ill patients). For the CI-S, if there is one (1) point or more difference in the two blinded reviewers scores, the two scores will still be averaged.

Supportive secondary endpoints will be evaluated that directly supplement the analysis of the primary endpoint as follows:

- The CI-CS for end of treatment with N-Acetyl-L-Leucine (Visit 4) versus baseline (Visit 2) and end of washout (Visit 6) versus end of treatment with N-Acetyl-L-Leucine (Visit 4) will each be summarized descriptively.
- Improvement in the primary and non-primary anchor test measures will be evaluated based on the change in the blinded raters' Clinical Impression of Severity (CI-S) between baseline (average for Visit 1 and Visit 2) and end of treatment with N-Acetyl-L-Leucine (average for Visit 3 and Visit 4) minus the change in CI-S between end of treatment with N-Acetyl-L-Leucine (average for Visit 5 and Visit 6). Statistical testing for the primary anchor test CI-S endpoint will be as for the primary endpoint. There will be no formal statistical testing of the non-primary test.
- Sensitivity measurement of change in performance on either the 9HPT-D or the 8MWT on a 3-point scale. Using the CI-CS outcome for the primary anchor test based on the data for **Visits 2** and **Visit 4**, any patient given a score of <0 on the CI-CS will be classified as worsened (-1). Any patient classified as 0 on the CI-CS will be classified no change (0). Any patient given a score of >0 on the CI-CS will be classified as improved (+1). A similar classification will use the CI-CS comparing the end of treatment with N-Acetyl-L-Leucine with end of washout based on the data for **Visits 4** and **Visit 6** and the difference between these scores calculated. The descriptive table will be similar to the primary endpoint. No statistical analysis will be performed.
- An evaluation of the CI-CS for the test (9HPT-D or 8MWT) that was not selected as the primary anchor test (i.e., the non-primary anchor test) will also be undertaken. There will be no formal statistical testing of these endpoints, however.

Bland-Altman plots in relation to videos from Visits 1 and 2, Visits 3 and 4, and Visits 5 and 6 will be produced to help inform the stability of the outcome evaluation and the disease itself at baseline, end of treatment and end of washout. The scatter plot for videos from Visits 1 and 2 will place the average CI-S outcome of the videos from Visits 1 and 2 on the x-axis and the difference between those on the y-axis. A y=0 line will be placed on the plot for reference purposes. Similar plots will be produced for videos from Visits 3 and 4 and videos from Visits 5 and 6. Additional secondary endpoints will investigate other measures of symptoms and quality of life. Descriptive statistics will be provided for these measures at each visit and also changes from baseline (Visit 2) to the end of treatment with N-Acetyl-L-Leucine (Visit 4), as well as end of treatment with N-Acetyl-L-Leucine (Visit 4) to the end of post-treatment washout (Visit 6) for the following measures:

- Spinocerebellar Ataxia Functional Index (SCAFI)¹⁶
- Scale for Assessment and Rating of Ataxia (SARA) score
- Quality of Life EQ-5D-5L for patients aged ≥18; EQ-5D-Y¹⁷ for patients aged <18 years
- Modified Disability Rating Scale (mDRS)
- Treating Physician Clinical Global Impression of Severity (CGI-S) at every visit
- Treating Physician Clinical Global Impression of Change (CGI-C) comparing end of treatment (Visit 4) to baseline (Visit 2), and end of washout (Visit 6) to end of treatment (Visit 4)
- Caregiver Clinical Global Impression of Severity (CGI-S) at every visit
- Caregiver Clinical Global Impression of Change (CGI-C) comparing end of treatment (Visit 4) to baseline (Visit 2), and end of washout (Visit 6) to end of treatment (Visit 4)
- Patient Clinical Global Impression Scales Impression of Severity (CGI-S) at every visit *if they are able*
- Patient Clinical Global Impression of Change (CGI-C) comparing end of treatment (Visit 4) to baseline (Visit 2), and end of washout (Visit 6) to end of treatment (Visit 4) *if they are able*

The SARA total score, the SCAFI total score, the individual SCAFI subtests: 9 Hole Peg Test with the Dominant Hand (9HPT-D), 8 Meter Walk Test (8MWT), and PATA test, will be evaluated statistically based on a single sample t-test or a single sample Wilcoxon Signed Rank test.

The individual SCAFI subtest: 9 Hole Peg Test with Nondominant hand (9HPT-ND), and the mDRS will be evaluated descriptively.

The CGI-S measures, and caregiver and patient CGI-C measures will be summarized descriptively. The physician's CGI-C measures will be analyzed as for the CI-CS primary endpoint.

The measures of the two indices (-5L and -Y) of the EQ-5D descriptive system and measures of the two indices (-5L and -Y) of the EQ-5D visual analogue scale (VAS) will be evaluated descriptively.

8.5.3 Exploratory Efficacy Endpoints

Sparse PK sampling will be collected to characterize the PK of N-Acetyl-L-Leucine in patients with GM2 Gangliosidosis.

8.6 Missing Data

The primary endpoint will utilize assessments based on single video recordings at the end baseline period (Visit 2), end of the treatment period (Visit 4), and end of the washout period (Visit 6). If the Visit 2 video is missing, the Visit 1 video will be used in its place. Similarly, if the Visit 4 and Visit 6 videos are missing, Visit 3 and Visit 5 videos will respectively be used in their place.

Analyses based on the mITT analysis set will utilize a last observation carried forward (LOCF) approach for missing videos at Visit 5 and Visit 6. For the primary endpoint CI-CS, this implies

¹⁶The 9 Hole Peg Test of the Dominant Hand (9HPT-D) and the 8 Meter Walk Test (8MWT), will be videoed for every patient at every visit except Visit 0

¹⁷ European Sites Only

that the CI-CS value for **Visit 4** to **Visit 6** will be assigned the value 0 (stable) if both videos at Visit 5 and Visit 6 are unavailable.

A sensitivity analysis will be undertaken to assess the robustness of the primary analysis of the primary endpoint in the mITT analysis set as follows:

If either video for Visit 3 or Visit 4 is available, but either video from Visit 5 and Visit 6 are unavailable, impute the value -1 (worsening) instead of 0 for the CI-CS for Visit 4 to Visit 6, unless the missingness is due to a "technical reason" (e.g. due to machine failure).

Additional methods to deal with missing data will be detailed in the SAP. Any changes from the SAP will be described and justified in the Clinical Study Report.

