8.10 Determination of Sample Size

It is postulated that N-Acetyl-L-Leucine will show effectiveness in 30% of patients and this success rate is viewed as being clinically important. Assuming that this group of patients will have scores that are evenly distributed across the values 1 and 2 for the primary endpoint and further that the remaining 70% of patients will have scores that are evenly distributed between the values -1, 0, and 1. The resulting mean score is 0.45 and the standard deviation (SD) for the primary endpoint under these assumptions is then 1.02. With 30 patients reporting on the primary endpoint, the study will have 76% power to detect a treatment benefit in a 5% one-sided one-sample t-test.

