5.6 Statistical analysis efficacy endpoints

The primary analysis population is the mITT for the primary and all secondary endpoints. Analyses of these endpoints based on the PPS will also be undertaken to provide supplementary information on efficacy. The ITT population will be used only for baseline summary tables.

Analyses of the primary endpoint based on the mITT population will utilise a last observation carried forward (LOCF) approach for missing/unreadable videos at Visit 5 and Visit 6. For the primary endpoint CI-CS, this implies that the CI-CS value for Visit 4 to Visit 6 will be assigned the value 0 (stable) if both videos at Visit 5 and Visit 6 are unavailable.

Also for the key secondary endpoint, Change in Severity Score based on Averaged Clinical Impression of Severity (CI-S), it is assumed that if both videos are missing/unreadable for the baseline (Videos from Visit 1 or 2), treatment (Videos from Visit 3 or 4), or washout (Videos from Visit 5 or 6) period, the change from one period to another will be assigned the value 0 (stable).

Clinical Study Reference: IB1001-202

A sensitivity analysis for missing data will be performed for the statistical analyses to compare patient's outcome on the primary outcome measure and their compliance throughout the study. The robustness of the primary analyses in the mITT analysis set will be assessed as follows:

• If either video for Visit 3 or Visit 4 is available but both videos for Visit 5 and Visit 6 are not available, then the value -1 (worsening) will be used instead of 0 for the CI-CS for Visit 4 to Visit 6 unless the missingness is due to a technical reason (MCAR, e.g. due to machine failure).

For each of the primary and secondary endpoints there will be separate descriptive statistical displays within the key subgroups as listed in Section 5.5.3 without any statistical analysis. For the subgroup presentations, only the mITT population will be used. Spaghetti plots will not be created for the subgroup analyses; these will be presented in forest plots (one for each endpoint, excluding the SARA -, SAFI - and mDRS subscores and excluding the EQ-5D-5L/Y), presenting the mean or (pseudo-)median with a 90% two-sided CI, using a stem at mean or median difference of 0, where applicable. Upon discretion of the programmer, the forest plots may be presented as two plots: one for Visit 4 versus Visit 2 and one for Visit 6 versus Visit 4.

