After the adjustments made for 8MWT and 9HPT as above, SCAFI total score will be calculated as follows:

The mean of the trial1 and trial2 scores are determined for each subtest/hand, and referred to as: $8MW_avg$, $9HPT-D_avg$, $9HPT-ND_avg$ and $PATA_avg$. In case a subtest is only performed once, this value is taken as the mean. Then, the 8MW and 9HPT performance times are converted to the same dimension as the PATA rate, as follows: $8MW_recipr = 1/8MW_avg$, $9HPT_recipr = (1/9HPT-D_avg + 1/9HPT-ND_avg)/2$. Note that 8MW and 9HPT performance times cannot be 0.

Then each is converted into a Z-score using the following algorithms:

- 8MW_zscore = (8MW_recipr BL(mean 8MW_recipr)) / BL(SD 8MW_recipr)
- 9HPT_zscore = (9HPT_recipr BL(mean 9HPT_recipr)) / BL(SD 9HPT_recipr)
- PATA zscore = (PATA avg BL(mean PATA avg)) / BL(SD PATA avg)

where BL means baseline value and SD means standard deviation. The mean 8MW_recipr and SD 8MW_recipr are determined using the SAF analysis population.

In case of missing values, the following applies:

- The cases with either 8MW, 9HPT (in one or both hands) or PATA tests not performed at all ("unable to perform due to physical limitations" or "not performed for other reason") are excluded from the calculation of baseline means.
- Only when an 8MW score, 9HPT score or PATA score is missing due to "unable to perform due to physical limitations", then a substitution will be applied as follows:
 - $\circ~$ When 8MW tests were not performed, then 8MW_recipr will be substituted by 1/1800~s.
 - When 9HPT tests were not performed: if only data for one hand is missing, then 9HPT_avg=3000 s for that specific hand; when data for both hands are missing, then 9HPT_recipr=1/3000 s.

• When PATA tests were not performed, then PATA_avg is substituted with 0. For agreement on "unable to perform due to physical limitations" or "not performed for other reason", the sponsor will be contacted. The missings created for 8MWT and 9HPT as stated above are considered "unable to perform due to physical limitations".

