According to the "SCAFI rating manual", the SCAFI total score is to be determined as the arithmetic mean of the 3 Z-scores. However, following explanation of IntraBio and [name], the SCAFI score needs to be calculated as the mean of the non-missing Z-scores. The SCAFI score can only be determined if at least one test is actually performed, i.e. in case all tests were imputed because of missing values, no SCAFI score will be determined. This contradicts the "SCAFI rating manual".

SARA

Clinical Study Reference: IB1001-202

The overall SARA score is reported as provided in the eCRF. For presentation of the subscore results, the individual results as provided in the eCRF will be used, where for the subscores finger chase, nose-finger test, fast alternating hand movements, heel-shin slide this is the average value for the two sides (left and right) as determined per eCRF.

mDRS

The mDRS composite score is calculated as a sum of the separate subscores divided by 24. If one of the subscores is missing, the mDRS composite score is missing as well. As compared to the official questionnaire, the eCRF allows values of 0 ('normal') for the subscores.

Laboratory

Laboratory safety data measurements that are denoted as smaller/larger than a certain value (e.g. < x.x), will be imputed with this value (e.g. x.x) for calculations of descriptive statistics. Listings will show the value as collected, and a footnote will be added to the summary tables for explanation.

Comments

The following data are either not collected or only collected as free text fields in the eCRF/database or lack relevant information in the database, and it is therefore necessary that these details are added in the programming code manually. The decisions to drive this manual coding may be documented and finalized during the BDRM but can already be maintained/discussed during the course of the trial for efficiency.

- The reason for video unavailability is recorded as free text field, and it needs to be deducted if any of these reasons consider a "technical issue". The sponsor will provide input.
- PATA score missing due to "unable to perform due to physical limitations" is not available as such in the database but needs to be deducted from a free comment field. The sponsor will provide input.

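### A missing Visit 4 video is replaced by the Visit 3 video whatever the reason, so loss of the anchor test on drug after Visit 3 can be scored on earlier, better performance, and no planned analysis tests this

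*Protocol*

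**What the plan says.** The primary endpoint is the CI-CS for Visit 2 to Visit 4 minus the CI-CS for Visit 4 to Visit 6 (Protocol 8.5.1, SAP 4.1.1).

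- **Substitution.** Protocol 8.6 uses Visit 1 for a missing Visit 2 video and continues: "Similarly, if the Visit 4 and Visit 6 videos are missing, Visit 3 and Visit 5 videos will respectively be used in their place". No reason for missingness is attached. SAP 5.6 does not restate the Visit 3 for Visit 4 swap, but its sensitivity rule presupposes it by requiring that either of those two videos be available.
- **Zero.** In the primary endpoint the value 0 is given to the Visit 4 to Visit 6 comparison only, "if both videos at Visit 5 and Visit 6 are unavailable" (SAP 5.6; Protocol 8.6 agrees).
- **Sensitivity analysis.** The 0 becomes -1 unless the reason is technical. SAP 5.6 applies this when both washout videos are missing; Protocol 8.6 words the trigger as either video.
- **Analysis set.** The mITT needs a video at Visit 3 or Visit 4 (Protocol 8.1.2, SAP 3.1.2).
- **Inability elsewhere.** For SCAFI, SAP 10.1 provides for tests not done because of physical limitations: "When 8MW tests were not performed, then 8MW_recipr will be substituted by" 1/1800 s, and a missing 9HPT hand is set to 3000 s.
- **Reasons.** "The reason for video unavailability is recorded as free text field" (SAP 10.1); the sponsor sorts out which entries are technical issues.

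Neither document says how the primary endpoint treats a patient who can no longer perform the anchor test.

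**The concern.** Visit 3 is at Day 28 (+7 days) and Visit 4 at Day 42 (+7 days), later still if Visit 4 is postponed for COVID-19. Loss of function in that interval is an on-drug outcome. If it leaves no ratable video, the plan puts the Visit 3 video in its place, both as the end of the treatment comparison and as the start of the washout comparison. The loss then appears in neither leg.

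Eligibility admits SARA scores up to 33 of 40 and gait subscores up to 7, so inability is a plausible event, and the SCAFI rule shows that the sponsor foresaw it. In a single-arm trial of about 36 mITT patients tested at one-sided 5%, a few such patients matter. The sensitivity analysis that should probe missing data addresses only the washout leg.

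**Working it through.** **Inputs.** Protocol 8.10: mean 0.45, SD 1.02, n = 30, one-sided 5% one-sample t-test, 76% power. Protocol 3.1.3: about 36 in the mITT. SAP 5.2: CI-CS runs from -3 to +3.

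**The plan's own figure.** Noncentrality = 0.45/1.02 × √30 = 2.42 on 29 df, which gives power of 76.3% against the stated 76%. It reproduces.

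**Scores for individual patients.** Assume that Visit 3 looks unchanged from Visit 2, and that inability would rate -3. The -3 is an assumption: SAP 5.2 defines that score by rater judgement and does not link it to inability.

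| Course | Plan | Planned sensitivity analysis | Loss rated -3 |
|---|---|---|---|
| Unable at Visits 4, 5 and 6 | 0 - 0 = 0 | 0 - (-1) = +1 | -3 - 0 = -3 |
| Unable at Visit 4, able again at Visit 6 | about 0 (Visit 6 is compared with Visit 3) | not triggered under the SAP wording | -3 - 3 = -6 |
| Unchanged at Visit 4, unable at Visits 5 and 6 | 0 - 0 = 0 | 0 - (-1) = +1 | 0 - (-3) = +3 |
| No video at Visit 3 or Visit 4 | not in mITT | not in mITT | not scored |

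In the first two rows the plan favours the drug. In the third it works against the drug.

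**Shift in the mean.** One patient among 36 scored -3 instead of 0 moves the mean by 3/36 = 0.083, or 0.083/0.45 = 19% of the planned effect. At -1 the shift is 1/36 = 0.028 (6%). At -6 it is 6/36 = 0.167 (37%).

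**Effect on the test.** Take 35 patients with mean m and SD 1.02, and one patient scored x.

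- Mean = (35m + x)/36
- Sum of squares = 34 × 1.02² + (35/36)(x - m)²
- SD = √(sum of squares/35)
- t = mean/(SD/6) on 35 df

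For m = 0.40 and x = -3: mean = 11/36 = 0.306, sum of squares = 35.37 + 11.24 = 46.61, SD = 1.154, t = 1.589, p = 0.061.

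| x | p at m = 0.40 | p at m = 0.45 |
|---|---|---|
| +1 (planned sensitivity analysis) | 0.009 | 0.005 |
| 0 (plan) | 0.013 | 0.007 |
| -1 | 0.022 | 0.012 |
| -2 | 0.036 | 0.021 |
| -3 | 0.061 | 0.037 |

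With the Wilcoxon fallback of SAP 5.6.1, on 35 normal-quantile scores with m = 0.40 and x = -3, p = 0.037.

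**The case against.** The strongest objection is that inability need not produce a missing video. Both anchor tests are to be filmed at every visit except Visit 0. SAP 10.1 keeps walks done with unallowable support because they bear on the video endpoint. Filming and rating of failed attempts may be covered in the CI-CS manual, the video-acquisition manual or the Video Review Charter, none of which is supplied. Part of the SCAFI unable category consists of supported walks and peg trials over 300 seconds, which raters may well see. The overlap with missing anchor videos is therefore unknown. This stands and limits how many patients can be affected. It does not close the gap, because SAP 10.1 also provides for tests not performed at all.

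A reader might infer that the zero hides on-drug deterioration. The documents do not support that for the primary endpoint, where the zero fills only Visit 4 to Visit 6. It works against the drug when function is lost only after stopping, as does replacing Visit 6 by Visit 5. Only the Visit 3 swap can conceal on-drug loss, and a Visit 3 video that already shows decline is scored as decline.

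A reader might also infer that one patient would overturn the trial. That needs m = 0.40, a score of -3 and the t-test together. Significance at 5% is kept at m = 0.45, at -2, or under Wilcoxon.

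The plan has some partial safeguards. The blinded data review (SAP 3.4) may reclassify reasons for missingness, the transferred rater data carry missing-data categories (SAP 9), and Visit 4 may be postponed but not skipped. None of these changes what is imputed.

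**Conclusion.** The concern holds in a limited form. As written, the Visit 3 swap ignores the reason for missingness and favours the drug for any patient who loses the anchor test on treatment after Visit 3 and has no ratable Visit 4 video. If the loss persists through washout, the one planned sensitivity analysis moves that patient a further point in the drug's favour. Loss before Visit 3, or at Visit 4 when the in-person Visit 3 was skipped and so not filmed, removes the patient from the mITT. No analysis tests the treatment leg.

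Each affected patient among 36 moves the mean by 0.028 to 0.083 if the loss is rated -1 to -3, or 6% to 19% of the planned effect. This assumes that Visit 3 looked unchanged, that the loss persists and that no ratable video exists. The number of such patients cannot be derived from the documents and may be zero, so neither a false-positive result nor a contradiction between SCAFI and CI-CS in any given patient can be claimed.

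**What to change.** 1. In Protocol 8.6 and SAP 5.6, state that the Visit 1, 3 and 5 substitutions and the value 0 apply to videos missing for technical or attendance reasons. State whether failed attempts are filmed and rated, and give the primary-analysis rule for a patient who could not perform the test.
2. Classify the free-text reasons before database lock as technical, attendance or physical inability, with visit and scores masked.
3. Add a prespecified sensitivity analysis in which physical inability on treatment receives an unfavourable Visit 2 to Visit 4 CI-CS, shown at -1, -2 and -3. Include patients otherwise dropped from the mITT for that reason. Set Visit 4 to Visit 6 to 0 if the patient is still unable, and state the value used if function returns.
4. Do not apply the -1 washout imputation to patients already unable at Visit 4. Align its trigger between the two documents.

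Fixed scores of -3 and +3 in the primary analysis are not needed. They would replace blinded rating and could give -6 for an unrelated injury.

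The cost is a SAP revision, a wording change in Protocol 8.6 and a review of reasons already collected. The downside is that a few extreme scores raise the SD slightly, and the added analysis may be less favourable to the drug.
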